| CTC grade ≥ 3 (QTcF > 500 msec) | Dose is interrupted until a cardiologist consult obtained. If QTcF >500 is confirmed by cardiologist, the patient is to be discontinue |

See Section 6.3.3 for further guidance on QTcF adverse events

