6.3.3.2 QT-related cardiology consultation / Holter monitoring

All patients will be asked to return on Day 22 for an ECG recording and PK sampling.

If at any visit a QTcF > 500 msec is observed, triplicate ECGs, each 2-3 minutes apart, need to be taken approximately 1 hour after the initial ECG. The mean QTcF from the triplicate ECGs will be determined. If the mean QTcF is > 500 msec, the patient has to postpone study treatment until a cardiologist has re-evaluated the ECG (this can be done by the central cardiologist). The re-evaluation needs to be done as soon as practical but within 7 days of the

initial abnormal ECG. If the cardiologist confirms a mean QTcF > 500 msec, the patient must be discontinued from the study. Otherwise and if the cardiologist confirms that at least one ECG shows a QTcF > 470msec, the cardiac assessments described for a confirmed QTcF > 470 msec needs to be followed.

If at Day 22 a QTcF / mean QTcF > 470 msec but \leq 500 msec is observed for the first time for a patient at a given dose level, the following steps need to be taken (please also refer to [Figure 6-2](#)):

A cardiology consultation must be sought as soon as practical but within 7 days of the initial abnormal ECG and prior to the next pasireotide LAR injection. The cardiologist must re-evaluate the ECG:

- If a QTcF > 470 msec is NOT confirmed, no further action needs to be taken.
- If a QTcF > 470 msec is confirmed, a cardiologist must perform a thorough examination (such as reviewing baseline ECG, concurrent medications and performing a cardiovascular examination, including at least a cardiac auscultation) to assess the patient for cardiovascular risk factors.
- If based upon the assessment by the cardiologist, the investigator considers that there is an acute cardiovascular safety risk and that the patient should not continue with study medication, the patient needs to be discontinued immediately (discontinuation criteria to be followed as described in [Section 7.1.3](#)).
 - If following the examination by the cardiologist, the investigator considers that there is no acute cardiovascular safety risk and that the patient could continue to receive study medication, a 24hr Holter ECG must be recorded at the next pasireotide LAR injection. The Holter-ECG must be started 30 min prior to an injection of study medication and a pre-dose PK sample will be taken.

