7.1.3.1 Criteria for premature patient withdrawal

Patients may voluntarily withdraw from the study or be dropped from it at the discretion of the investigator at any time. Patients may be withdrawn from the study if any of the following occur:

- Adverse event(s) [including abnormal laboratory value(s) and abnormal test procedure result(s)]
- Protocol deviation (including but not limited to, new therapy for acromegaly, and discovery of patient ineligibility)
- Patient withdrew consent

- Lost to follow-up
- Administrative problems
- Death
- Disease progression
- Pregnancy
- Treatment duration completed as per protocol

The investigator must also inform the premature withdrawal to Novartis, if this occurs during the core period.

In addition to the general withdrawal criteria, the following **study specific criteria** will also require study treatment discontinuation:

- Patients experiencing unacceptable toxicity, as described in [Table 6-2](#), [Table 6-3](#).
- Patients unable to tolerate the lowest dose (20 mg) as per [Section 6.3](#).
- Patients with > 28 consecutive days of treatment interruption (either due to tolerability, investigator decision or patient compliance)
- Uncontrolled diabetes mellitus, consistently high glucose values FPG \geq 240 mg/dL (13.3 mmol/L) or HbA1c value \geq 10 % despite prior appropriate management and prior dose adjustment of the study drug,
- Patients experiencing adverse events in QTc:
 - a confirmed QTcF $>$ 470msec and discontinuation recommended by a cardiologist, or
 - Mean QTcF $>$ 500 msec measured by triplicate ECGs
 - Significant arrhythmia findings from Holter monitoring such as:
 1. Any ventricular or supra-ventricular tachyarrhythmia associated with symptoms of hemodynamic compromise
 2. Sustained ventricular tachycardia ($>$ 30 sec) irrespective of symptoms
 3. Recurrent non-sustained ventricular tachycardia (\geq 3 beats) during any 24-hour monitoring period
 4. Torsades de Pointes
 5. Cardiac arrest
 6. Pause $>$ 5 seconds
 7. Second or third degree AV block
 - New occurrence of clinically significant/symptomatic bradycardia, or
 - Increased risk of QT prolongation by use of QT prolonging medication, or
 - Hypokalemia ($<$ 3.5 mmol/L) or hypomagnesaemia ($<$ 0.7 mmol/L) confirmed by repeat testing that is either a new finding or accompanied by vomiting or diarrhea and not corrected by treatment.
- Patients experiencing the abnormal hepatic criteria below:

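### Section 7.1.3.1 requires a stop at a triplicate mean QTcF above 500 msec without cardiologist confirmation, which conflicts with Section 6.3.3.2 and Table 6-3 when the cardiologist does not confirm the value

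*Protocol*

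**What the plan says.** Three places in the protocol deal with a QTcF above 500 msec.

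- **Section 7.1.3.1 (premature withdrawal).** The study-specific criteria are introduced as ones that "will also require study treatment discontinuation". One of them is a mean QTcF above "500 msec measured by triplicate ECGs". No confirmation or cardiologist is mentioned. The bullet just before it is conditional: it asks for a confirmed QTcF above "470msec and discontinuation recommended by a cardiologist, or". The same list opens with "Patients experiencing unacceptable toxicity, as described in" Tables 6-2 and 6-3, so it also brings in the Table 6-3 rule.
- **Section 6.3.3.2 (QT procedure).** A QTcF above 500 msec at any visit leads to triplicate ECGs about an hour later, and their mean is taken. Then: "If the mean QTcF is > 500 msec, the patient has to postpone study treatment until a cardiologist has re-evaluated the ECG". The re-evaluation is due within 7 days of the first abnormal ECG. The outcome is stated as: "If the cardiologist confirms a mean QTcF > 500 msec, the patient must be discontinued from the study". The alternative branch begins "Otherwise and if the cardiologist confirms that at least one ECG shows a QTcF > 470msec" and leads to the assessments set out for a confirmed value above 470 msec.
- **Table 6-3 (in Section 6.3.1).** For grade 3 or higher, the dose is interrupted until a cardiologist has been consulted. After that: "If QTcF >500 is confirmed by cardiologist, the patient is to be discontinue".

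**The concern.** The withdrawal list and the QT procedure start from the same measurement, a triplicate mean above 500 msec, but attach different conditions to stopping. The protocol does not say which takes precedence. Section 6.3.3.2 refers readers to Section 7.1.3 for the discontinuation criteria, so a site that follows the QT procedure is sent to the list that differs from it.

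This is the highest QTcF threshold in the protocol, for a drug whose QT effect Section 1.2.1.2 describes as shown in two thorough QT studies. Two sites could act differently on identical ECGs while each follows the text. Whichever rule is intended, following the other would either stop a patient whom the plan means to keep or keep a patient whom it means to stop. The stop also has lasting consequences, because Section 7.1.3.1 bars patients who withdraw early in the core phase from the extension.

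**Working it through.** The protocol states no figure on this point, so the main check is a comparison of the rules. Take a patient whose triplicate mean QTcF is above 500 msec and follow each place in the text.

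| Cardiologist's reading | Section 7.1.3.1 | Section 6.3.3.2 | Table 6-3, grade 3 or higher | Same end state? |
|---|---|---|---|---|
| Not yet available | Discontinuation criterion met as worded | Postpone treatment | Interrupt dose | Instructions differ, but none allows a further dose |
| (a) Mean above 500 msec confirmed | Discontinue | Discontinue | Discontinue | Yes |
| (b) Above 500 not confirmed, at least one ECG above 470 confirmed | Discontinue | Assessments for values above 470 msec; continuation or discontinuation possible | Condition for stopping not met | No |
| (c) Neither confirmed | Discontinue | No stop required | Condition for stopping not met | No |

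The end states therefore differ in (b) and (c) and agree in (a). Table 6-3 speaks of QTcF and does not mention the triplicate mean. The conflict between 7.1.3.1 and 6.3.3.2 does not depend on it.

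**Reach into the primary endpoint.** Protocol Section 10.4.3 counts a patient who discontinues before the Month 3 assessment as a non-responder. For this wording to change the primary result, three things must hold together:

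1. the patient falls in (b) or (c);
2. the stop comes before the Month 3 assessment;
3. the patient would otherwise have been a responder.

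One such patient is 1/33 = 3.0 percentage points, with the 33 randomized patients given in the SAP (Section 2). Section 10.8 compares the lower limit of the Clopper-Pearson two-sided 90% interval with 10%. For x responders among n = 33, that limit is the 5% quantile of a Beta(x, n − x + 1) distribution:

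- x = 6: 8.2%
- x = 7: 10.4%
- x = 8: 12.7%
- x = 9: 15.0%

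The dropout-adjusted rate expected in Section 10.8 is 27%, and 0.27 × 33 = 8.9, or about 9 responders. From 9, losing one responder gives 12.7% and losing two gives 10.4%. Both are still above 10%. A single patient decides the comparison only if the count lies exactly at 6 versus 7.

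**The case against.** The strongest reply is that the bullet in 7.1.3.1 is shorthand. Triplicate ECGs are described only in 6.3.3.2, so a site can apply the bullet only by entering that procedure, which ends with the cardiologist. The list in 7.1.3.1 also brings in Table 6-3, whose rule is confirmation, and the notes to Tables 6-2 and 6-3 send QT management to Section 6.3.3. Section 7.1.3.1 does not say whose reading counts either. ECGs go to a central reader (Section 7.2.2.5.1), and 6.3.3.2 allows the re-evaluating cardiologist to be the central one. If the re-evaluated value is the one of record, an unconfirmed mean would never meet the 7.1.3.1 criterion.

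This reading is possible, but the protocol does not state it. The neighbouring bullet for the lower threshold writes in both confirmation and the cardiologist, and the bullet for the higher threshold writes in neither. A reader may fairly take the difference as intended. Because the list also brings in Table 6-3, it holds a conditional and an unconditional rule side by side.

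The rest of the reply limits the point and stands:

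- A reader might infer that any triplicate mean above 500 msec leads to two different outcomes. It does not, because a confirmed value ends in discontinuation everywhere.
- A reader might infer that one of the rules lets a patient be dosed on an unreviewed value. It does not, because treatment is held until the cardiologist has read the ECG.
- A reader might infer that 6.3.3.2 simply lets the unconfirmed patient carry on. If a value above 470 msec is confirmed, that pathway brings a cardiologist's examination and Holter monitoring where treatment may continue, and it can still end in discontinuation.

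**Conclusion.** The point holds in a limited form. Section 7.1.3.1 as worded contradicts 6.3.3.2 and Table 6-3 when a triplicate mean above 500 msec is not confirmed by the cardiologist. When it is confirmed, they agree. The protocol foresees non-confirmation, since 6.3.3.2 has a branch for it, but gives no frequency. It is likely low.

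A stronger reading is that the primary conclusion hangs on this wording, because 6 and 7 responders of 33 fall on either side of the 10% limit. The documents do not support that. It would take an unconfirmed case, a stop before Month 3, a patient who would otherwise respond, and a count exactly at that boundary. At the expected count of about 9, the lower limit is 15.0%. The reason to act is that sites hold inconsistent safety instructions. The endpoint is not the reason.

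The conclusion rests on reading 7.1.3.1 as written, without an implied confirmation step. Figure 6-2 is not shown, so whether it agrees with either section is unknown. Nothing here says which rule is clinically right.

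**What to change.** Reconcile Section 7.1.3.1 with Section 6.3.3.2 and Table 6-3, and check Figure 6-2 against them. One condition for discontinuation at a QTcF above 500 msec should appear in all of them. It should say whether cardiologist confirmation is needed and, for clarity, whether the value that counts is the triplicate mean and whose reading of it applies. The choice of condition is the sponsor's clinical decision. The cost is protocol wording only, with no change to the design, sample size or analysis.

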2.2 Rationale for the study design

This study is a multi-center, open label, randomized phase II study in Japan evaluating the efficacy, safety, PK and pharmacodynamics of pasireotide LAR in patients with active acromegaly and pituitary gigantism.

With reference to the design of [CSOM230C2110] in western patients with acromegaly, the starting doses of this study will be fixed at 20 mg, 40 mg, and 60 mg during the first 3 months. The response rate is defined as the proportion of responders (responder defined as the reduction of mean GH levels to $< 2.5 \mu\text{g/L}$ and normalization of IGF-1 to within normal limits). The response rates at 20 mg, 40mg and 60mg in [CSOM230C2110] were comparable (30% at 20mg, 41.7% at 40mg, and 38.5% at 60mg). According to [CSOM230C2305], early response was observed at 3 months. And the response rate at 3 months was almost same as that at 6 and 12 months. After 3 months study treatment, the efficacy of pasireotide LAR in overall population will be assessed. As in the case of [CSOM230C2305], it is permitted to increase the dose (up to 60 mg) after the first 3 months of study treatment if biochemical parameters show a mean GH level $\geq 2.5 \mu\text{g/L}$ and/or IGF-1 $> \text{ULN}$ (age and sex related). In the event of any problem with tolerability, it is permitted to reduce the dose down to 20 mg at any time. Core and extension treatment periods were set with reference to [CSOM230C2305].

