4.1 Description of study design

A total of 30 eligible patients will be enrolled. The enrolled patients will be randomized to one of 3 doses of pasireotide LAR (20 mg, 40 mg, or 60 mg) in a ratio of 1:1:1. Randomization will be stratified by prior medications (e.g. somatostatin analogues, dopamine agonists or GH receptor antagonists), (yes or no). Intramuscular administration of pasireotide LAR will be repeated every month (1 month = 28 days) for 12 months in core phase. It is permitted to increase the dose up to 60 mg in a patient showing the following biochemical test results after 3 and 6 months of study treatment: mean GH levels $\geq 2.5 \mu\text{g/L}$ and/or IGF-1 $> \text{ULN}$ (age and sex related). In the event of any problem with tolerability, it is permitted to reduce the next lower dosage level at any time. After 3 months of study treatment, the primary endpoint (proportion of patients with a reduction of mean GH levels to $< 2.5 \mu\text{g/L}$ and normalization of IGF-1 to within normal limits) will be evaluated.

Patients with a reduction of mean GH levels to $< 2.5 \mu\text{g/L}$ and normalization of IGF-1 at the end of the 12-month study treatment will be enrolled in an extension phase of study treatment. Patients with a mean GH level $\geq 2.5 \mu\text{g/L}$ and/or IGF-1 $> \text{ULN}$ at the end of the 12-month study treatment may be enrolled in an extension phase of study treatment if the extended study treatment is thought to be clinically beneficial for them by the investigator. Patients will receive pasireotide LAR in the extension phase until unacceptable toxicity appears or until the medication is commercially available or until the pasireotide LAR development program is discontinued whichever comes first.

Patients, who participate in the extension phase, will receive a 13th injection of the pasireotide LAR, the Visit 779 (Study completion) will be their last visit.

Figure 4-1 Study design

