6.1.4 Guidelines for continuation of treatment

Patients may continue treatment provided no tolerability issues are present (See [Section 6.3](#)) and criteria for discontinuation are not met (see [Section 7.1.3](#)).

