6.3 Dose modifications

6.3.1 Dose modification and dose delay

Dose up-titration

Dose increases is permitted after the first three months of treatment (steady-state reached) if biochemical parameters show a mean GH level ≥ 2.5 $\mu\text{g/L}$ and/or IGF-1 $>$ ULN (age and sex related) and there are no tolerability issues (see [Table 6-1](#)). Patients on the 20 mg arm with a mean GH level ≥ 2.5 $\mu\text{g/L}$ and/or IGF-1 $>$ ULN (age and sex related) after the Month 2.75 (Visit 11) GH and IGF-1 assessment will have their dose increased to 40 mg at Month 3 (Visit 12), if there are no tolerability issues. Patients on the 40 mg arm with a mean GH level ≥ 2.5 $\mu\text{g/L}$ and/or IGF-1 $>$ ULN (age and sex related) after the Month 2.75 (Visit 11) GH and IGF-1 assessment will have their dose increased to 60 mg at Month 3 (Visit 12), if there are no tolerability issues. At Month 7 (Visit 16), patients receiving 20 mg and 40 mg doses with mean GH level ≥ 2.5 $\mu\text{g/L}$ and/or IGF-1 $>$ ULN (age and sex related) after the Month 6 (Visit 15) GH and IGF-1 assessment will have their dose increased to 40 mg and 60 mg, respectively, if there are no tolerability issues. Patients receiving the 60 mg dose at Month 3, 6 or 9 with a mean GH level ≥ 2.5 $\mu\text{g/L}$ and IGF-1 $>$ ULN (age and sex related) will be discontinued from the study unless clinical benefit has been observed as per the investigator's judgment.

Patients that have a mean GH level < 2.5 $\mu\text{g/L}$ and IGF-1 \leq ULN (age and sex related) on current therapy after Month 3 and/or Month 6 will be kept on their current dose.

After Month 12, the timing of the dose adjustments will be based on GH and IGF-1 values, at the investigators discretion but must include duration of at least 3 months on a current dose prior to up-titration and no tolerability issues are present. Patients receiving the 60 mg dose after Month 12 with a mean GH level ≥ 2.5 $\mu\text{g/L}$ and IGF-1 $>$ ULN (age and sex related) will be discontinued from the study unless clinical benefit has been observed as per the investigator's judgment.

Dose down-titration

Dose reduction is due to lack of tolerability (refer to [Table 6-2](#) and [Table 6-3](#)) will be allowed as one dose level reduction at a time (i.e. from 60 mg to 40 mg or from 40 mg to 20 mg) If tolerability issue is resolved, increase dose to that prior to the dose reduction unless investigator opinion to remain on current dose.

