 - ALT or AST $>$ 3 x ULN and Total Bilirubin \geq 2 x ULN and ALP $<$ 2 x ULN
 - ALT or AST $>$ 5 x ULN and \leq 8 x ULN persistent for more than 2 weeks

- ALT or AST > 8 x ULN
- Lack of efficacy: during the core phase treatment period, patients with GH level > 2.5ug/L and/or IGF-1 > ULN (age and sex related) be discontinued from the study unless clinical benefit has been observed as per the investigator's judgment.

Patients who withdraw prematurely from the core phase cannot participate in the extension phase.

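### The core-phase lack-of-efficacy stop in Protocol 7.1.3.1 contradicts the dose increase that 6.3.1 orders for tolerating 20 and 40 mg patients with no judged clinical benefit

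*Protocol*

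**What the plan says.** Protocol 7.1.3.1 introduces a list of study-specific criteria that "will also require study treatment discontinuation". The lack-of-efficacy item in that list, for the core phase, reads: "GH level > 2.5ug/L and/or IGF-1 > ULN (age and sex related) be discontinued from the study unless clinical benefit has been observed". The investigator judges whether there is benefit. The item names no dose, visit or start time. Protocol 6.1.4 allows treatment to continue if there is no tolerability problem "and criteria for discontinuation are not met", and refers to 7.1.3 for those criteria.

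Protocol 6.3.1 treats the same laboratory result differently. A 20 mg patient with GH at or above 2.5 µg/L and/or IGF-1 above ULN at Month 2.75 "will have their dose increased to 40 mg at Month 3 (Visit 12), if there are no tolerability issues". A 40 mg patient goes to 60 mg on the same terms. At Month 7, on the Month 6 result, patients on 20 and 40 mg "will have their dose increased to 40 mg and 60 mg, respectively, if there are no tolerability issues". The only core-phase efficacy stop in 6.3.1 is for "Patients receiving the 60 mg dose at Month 3, 6 or 9 with a mean GH level" at or above the cut-off and IGF-1 above ULN, with the same clinical-benefit exception.

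The design sections agree with 6.3.1. Section 2.2 says "it is permitted to increase the dose (up to 60 mg) after the first 3 months of study treatment", and 4.1 says "It is permitted to increase the dose up to 60 mg in a patient showing the following biochemical test results". Section 6.1.1 and SAP 2 repeat this.

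Three rules carry a stop through to the results. A core-phase withdrawal bars entry to the extension (7.1.3.1). Core-phase response rates keep discontinued patients in the denominator, whereas extension rates count them only at visits they reached (SAP 4.1.10). A patient who stops before the Month 3 assessment is a non-responder (Protocol 10.4.3, SAP 4.1.9).

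**The concern.** A tolerating 20 or 40 mg patient who is uncontrolled, and in whom the investigator sees no clinical benefit, must be up-titrated under 6.3.1 and stopped under 7.1.3.1. No text says which rule prevails, and 6.1.4 leans towards the stop. Yet a patient without benefit on a low dose is an obvious candidate for more drug.

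At stake is who stays on treatment after Month 3. That decides who can respond at Months 6, 9 and 12 and who enters the extension. It also decides who contributes Month 12 tumor volume and later safety data. If sites read the two sections differently, these summaries would mix two treatment policies.

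**Working it through.** **1. The two rules side by side (core phase, no judged clinical benefit)**

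| Patient | 6.3.1 | 7.1.3.1 | Relation |
|---|---|---|---|
| 20 or 40 mg, tolerating, one or both markers uncontrolled, Month 3 or 7 decision | Increase dose | Stop | Opposite orders |
| 60 mg, both uncontrolled, Month 3, 6 or 9 | Stop | Stop | Agree |
| 60 mg, one uncontrolled | No stop triggered | Stop | Differ in scope (*and* versus *and/or*) |
| GH exactly 2.5 µg/L | Counts as uncontrolled | Does not count | Differ in cut-off (≥ versus >) |

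Both inclusion routes (5.2, 3a and 3b) require raised IGF-1. With no start time, the item would catch any patient not yet controlled at the first on-treatment sample. That can hardly be intended. The item reads most plausibly as a loose summary of the 60 mg stop.

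**2. The plan's own figure (Protocol 10.8)**

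Expected rate: 0.30 × 0.90 = 27%, and 30 × 0.27 = 8.1, so 8 responders. The Clopper-Pearson 90% lower limit is 14.0% for 8/30, 11.5% for 7/30 and 9.1% for 6/30. The stated criterion of at least 10% is met at the expected rate. Aligning the two sections changes nothing here.

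**3. Size of the uncontrolled group (a ceiling)**

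Assume 33 patients split 11 per arm, so 22 at 20 or 40 mg. With 10% dropout, 22 × 0.9 = 19.8 are on study at Month 3. Uncontrolled:

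- plan rate of 30%: 19.8 × 0.70 = 13.9;
- phase I arm rates of 30% and 41.7%: 9.9 × 0.70 + 9.9 × 0.583 = 12.7;
- phase III crossover rate of 17.3%: 19.8 × 0.827 = 16.4.

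These figures precede the tolerability and clinical-benefit exemptions. The documents do not give the number left after them.

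**4. Effect per patient on Months 6, 9 and 12**

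Each stopped patient who would have responded after up-titration costs 1/33 = 3.0 points. For example, 10/33 = 30.3% (exact 95% CI 15.6 to 48.7) becomes 9/33 = 27.3% (13.3 to 45.5). Counting stopped patients as non-responders after Month 3 is an inference, because the explicit rule in SAP 4.1.9 covers Month 3 only.

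**5. Direction in the extension**

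Illustration with N = 30 and no dropout: 9 responders at Month 3 and 14 uncontrolled at 20 or 40 mg (20 × 0.70). A share *f* of the 14 is stopped, and a share *c* of the 14 would respond after an increase. Both shares are assumed.

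- Core rate: (9 + 14c)/30 without stops, (9 + 14c(1 − f))/30 with them.
- Extension rate if everyone else enters and keeps the same status: (9 + 14c(1 − f))/(30 − 14f) with stops.

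| f | c | Core fall (points) | Extension rate, no stops → stops |
|---|---|---|---|
| 0.25 | 0.1 | 1.2 | 34.7% → 37.9% |
| 0.5 | 0.2 | 4.7 | 39.3% → 45.2% |
| 1 | 0.3 | 14.0 | 44.0% → 56.2% |

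The extension rate rises when c < (9 + 14c)/30, that is c < 9/16 = 56%. Section 4.1 admits uncontrolled patients to the extension only if the investigator expects benefit. Some stopped patients would therefore not have entered anyway, so the rise would be smaller and need not occur.

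The documents give no conversion rate. The only related figure is the phase III net change from 30.1% at Months 3 and 6 to 31.4% at Month 12, or 1.3 points.

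**6. Month 3**

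Under 6.3.1 the decision rests on the Month 2.75 result and takes effect at Visit 12, when the Month 3 GH profile and IGF-1 are also taken before dosing. A stop at that point leaves the primary endpoint essentially intact. The literal 7.1.3.1 item has no start time, however. GH is sampled from Day 22 (Table 7-3) and IGF-1 also before Month 3 (Table 7-1). If a share *g* of eventual responders were stopped early, the expected rate would be 27% × (1 − g): 23.6% at g = 0.125 and 20.3% at g = 0.25. The chance of at least 7 of 30 responders would fall from 74% to 58% or 41%. Nothing in the documents suggests any value of *g* above zero.

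**The case against.** The strongest reply is that no competent site would be misled. Section 6.3.1 is specific by dose and visit, four other places describe titration, and the clinical-benefit exception lets an investigator keep a patient on treatment. Some of those places say only that an increase is permitted, so a mandatory stop could be said to override it.

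Much of this stands. Titration is clearly the intent, and the conflict reaches only tolerating 20 or 40 mg patients with no judged benefit. But the arm-specific sentences in 6.3.1 order the increase without any benefit condition, so the exception does not reconcile the rules for that group. Nor does any text give 6.3.1 precedence.

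Two stronger readings are tempting. A reader might take the 12.7 to 16.4 patients as the number affected. The documents do not support that: those figures size the uncontrolled group before the exemption that decides whether a conflict exists. A reader might also infer that the Month 3 primary result is compromised. That would need stops on early pharmacodynamic samples, which 6.3.1 does not call for and no document reports.

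Existing safeguards also count. SAP 5.3 already summarizes the primary reason for core-phase discontinuation, SAP 5.7 counts dose increases, and SAP 5.1 and 5.9.2.2 provide listings and individual GH and IGF-1 plots.

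**Conclusion.** The contradiction is real and 7.1.3.1 is wrong as written. It is a minor internal inconsistency, not a design choice. Its practical reach is unknown and may be zero.

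If 20 or 40 mg patients were stopped instead of up-titrated, the Month 6, 9 and 12 rates could fall by 3.0 points per lost responder, assuming 33 in the denominator and non-response after stopping. The Month 18 and 24 rates could move the other way, subject to who would have entered the extension. Month 12 tumor volume and later safety summaries also depend on who continues. It would therefore be too narrow to say that only Months 6 to 12 are exposed. It would be too strong to say that any reported rate is biased, because no document shows that the literal rule was applied. A Month 3 effect is unlikely if sites acted on the Month 2.75 result, but the wording does not exclude it. The sample size is unaffected.

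**What to change.** Restrict the lack-of-efficacy item in 7.1.3.1 to patients on 60 mg at Month 3, 6 or 9, keep the clinical-benefit exception, and cross-refer to 6.3.1. The reference in 6.1.4 then leads to the aligned rule. Take the marker condition (both markers) and the GH cut-off (≥ 2.5 µg/L) from 6.3.1, and ask the sponsor to confirm that choice, since the documents do not show which version was meant at 60 mg. The cost is one sentence. The Month 12 analysis is already reported, so this corrects the record and changes no past decision.

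Optionally, in the final CSR, extend the SAP 5.3 summary with dose and marker status (GH only, IGF-1 only, both) for core-phase patients whose recorded reason for stopping was lack of efficacy. Do not infer the reason from the last laboratory values; if the recorded reasons do not identify lack of efficacy, say so. If any patient stopped at 20 or 40 mg without up-titration, give the Month 6, 9 and 12 rates with only those patients counted as responders, as an upper bound, and note that the effect at Months 18 and 24 may run the other way. Leave 60 mg patients as they are, since they have no higher dose. If there are no such patients, state that the conflict had no effect through such stops. The stop reason, dosing records and central GH and IGF-1 values are already collected.
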